7.3 Group assignment

The group assignment in the sub-protocols is hidden with the help of a lot in a sealed envelope, which is drawn under the supervision of the study director. The test subject number and the application are noted on this lot. The examiner sets the exam condition and only announces the subject number to the other examiners. At the end of the entire data collection, this auditor pools the data sets according to the application.

7.4 Discontinuation of study participation

If a participant withdraws from the study, the lot of the allocation is returned to the pot in a new envelope and a new participant is sought.

The already completed consent form is stored in the locked filing cabinet, data that has already been collected is stored, but is not included in the further data analysis of the study.

The conditions for the termination of the experiment were described in chap. 5.4.

There is no disadvantage for the participants if they discontinue their participation in the study.

8 STUDY INTERVENTION

8.1 Medical Product ID

8.1.1 Intervention Product

Zamar Therapy

Zamar Therapy is a certified medical device according to European directives (Directive 93/42/EEC and ISO 13485:2012). The temperature can be reduced from -5.0°C to $+45^{\circ}\text{C}$. The maximum adjustable treatment time is 1 hour. Cuffs ensure optimal contact with the corresponding body region. A coolant circulates continuously between the device and the man's boot.

This device is used for the following indications: treatment of the musculoskeletal system (contusions, contractures, lesions of the second degree, hematomas), tendinogenic system (tendinitis, tenosynovitis, tendinopathy), bone-cartilage system (contusions, post fractures), capsuloligamentary system (sprains, torsions, Contusions of ligaments), postoperative, aesthetic surgery and to accelerate recovery time.

In this study, temperatures of $+8^{\circ}\text{C}$ and thermoneutral temperatures ($+32^{\circ}\text{C}$) are used for 20 minutes.

Fig. 1: Zamar Therapy (www.zamarmedical.com)

Securing the test subjects

The temperature of 8°C is a cooling temperature commonly used in the literature (cf. Ascensao et al., 2011; Bailey et al., 2007; Crystal et al., 2013; Delextrat et al., 2013; Ingram et al., 2009; Jakeman et al., 2009; King et al., 2009; Leal et al., 2011; Paddon-Jones et al., 1997; Pointon et al., 2011; Pointen et al., 2012; Sellwood et al., 2007; Yanagisawa et al., 2003). Nevertheless, the test subjects can stop the cold treatment at any time if they feel unwell.

During the maximum and submaximal loads, the test subjects go to their personal performance limit. Although they are motivated by the examiners, they are not encouraged to exceed the personal performance threshold. The test subjects can be used in case of discomfort or if the personal performance limit is reached, stop the loads at any time. Furthermore, 2 examiners will be next to the subject during the jumping load in order to be able to catch him/her in case of circulatory problems. An emergency kit is available at all times during the examinations (see Chapter 3.7. Risk/ Benefits).

SUPSI

8.1.2 Packaging, labeling and use

ICH: Also include a description of the dosage form, packaging, and labelling of the investigational product(s).

Zamar Therapy is a certified medical device according to European directives (Directive 93/42/EEC and ISO 13485:2012).

8.1.3 Storage

The Zamar Therapy must be stored inside a room. The equipment is therefore located all year round in a closed room with room temperature and low humidity.

8.2 Administration of the experiment (ICH/IT 6.4.4)

Since no medication or invasive methods are used, chap. 8.2 - 8.4 and referred exclusively to chapter 9.

8.2.1 Experimental intervention

ICH: Description of and justification of the treatment(s) to be administered, including the name(s) of all the product(s), the dose(s), the dosing schedule(s), the route/mode(s) of administration, and the treatment period(s), including the follow-up period(s) for subjects for each investigational product treatment/trial treatment group/arm of the trial.

Cooling application of + 8°C for 20 min on the right thigh

8.2.2 Control Intervention

ICH: Description of and justification of the treatment(s) to be administered, including the name(s) of all the product(s), the dose(s), the dosing schedule(s), the route/mode(s) of administration, and the treatment period(s), including the follow-up period(s) for subjects for each investigational product treatment/trial treatment group/arm of the trial.

Thermoneutral application of + 32 °C for 20 min on the right thigh

8.3 Can / Device modifications

(SPIRIT #11b)

8.4 Compliance with study Intervention

(ICH/E6 6.6.3; AGEK Checklist 2, item 2; SPIRIT #11c)

ICH: Procedures for monitoring subject compliance.

Subjects are motivated to perform MVIC and jump height measurement to keep their compliance high.

8.5 Follow-up treatment of eliminated participants

(ICH/E6 6.5.3; AGEK 9.2; SPIRIT #18b)

I: b) The type and timing of the data to be collected for withdrawn subjects. d) The follow-up for subjects withdrawn from investigational product treatment/trial treatment.

Data already collected from eliminated participants will be stored, but will not be included in the further data analysis of the study.

There is no disadvantage for the participants if they discontinue their participation in the study and no further interventions are necessary for follow-up treatment.

If study participation was due to an injury occurred during study participation,

SUPSI

is aborted, it will be recorded and reported to the sponsor investigator (head of the research laboratory), study leader and supervisor of the study. Furthermore, the report is sent to the public liability insurance of Thim van der Laan University College Physiotherapy in Landquart.

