3.7 Risk/ Benefits

(ClinV, Appendix 4, 3.5; Type 25d2; ICH/EG6.2.3; AGEK 11.1; SPIRIT #Ga; MD: ISO 14155 Annex A & 150 14971)

ICH: Summary of the known and potential risks and benefits, if any, to human subjects.

For the subjects, there is a minimal risk of overload during the maximum jumping exercise for 1 min and the MVIC 60% of the ventral thigh muscles (1 min). The rehearsals are expressly informed that they have reached the maximum or submaximal load at any time. Furthermore, 2 examiners will be next to the subject during the 1 min jump load to support him/her in case of circulatory problems

SUPSI

to be able to absorb it. A fully equipped emergency kit is in the examination room at all times during the examinations. In the case of circulatory problems due to hypoglycaemia, the examination room also includes dextrose, chocolate, and ®Coca Cola Ltd. available. The test subjects are also advised to complete the test well nourished in order to minimise the risk of hypoglycaemia. A fully functional and always accessible defibrillator (Lifepak Express Defibrillator, reaplus.ch) is located in our institution. This information is communicated to the test persons (subject information).

Furthermore, any injuries to the musculoskeletal system were defined as an exclusion criterion in order not to provoke a relapse of a past injury.

More information on securing the test subjects can be found in chap. 8.1.1.

The test subject does not derive direct benefits from participating in the study.

SUPSI

3.8 Justification of the choice of population (ClinO, Art 25d4, Art. 15-17; I/IT 6.2.6; AGEK 11.2) ICH: Description of the population to be studied.

This series of studies will be conducted with healthy young volunteers. The risk of injury is considered low in this test subject population.

Inclusion Criteria

- Young healthy adults aged 18 - 30 years
- No surgical interventions on the musculoskeletal system in the trunk area and lower extremities
- Injuries to the trunk and/or lower extremities that occurred more than 1 year ago and no longer cause symptoms
- Anti-conception drugs

Exclusion criteria

- Current injuries of any kind affecting the trunk and/or lower extremities
- Injuries to the torso and/or lower extremities that occurred less than 1 year ago
- Injuries to the trunk and/or lower extremities that occurred more than 1 year ago and are still causing symptoms.
- Fear of cooling intervention
- Taking medication of any kind (even self-purchased)

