9.2.5 Collection of data in case of early termination of studies

For the participants, there is no disadvantage in the event of an (arbitrary) discontinuation of study participation and no further interventions are necessary for follow-up treatment.

However, if the study participation was discontinued due to an injury occurred during the study participation, this will be recorded and reported to the sponsor investigator (head of the research laboratory), study leader and supervisor of the study. The report is then sent to the business liability insurance of Thim van der Laan University College Physiotherapy in Landquart.

The following are recorded:

- Date and time of the incident
- Course of the incident
- Persons involved & witnesses Study
- ID (assigned by the CEC)
- Personal details of the person concerned (if not previously recorded)

SUPSI

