11.2 Sample Size

The planned number of 20 subjects (project A), or 20 subjects (Project B) correspond to the group sizes of the comparable cooling studies (cf. (Ascenso et al. 2011, Bailey et al. 2007, Crystal et al. 2013, Rowsell et al. 2009, De Pauw et al. 2014, Guilhem et al. 2013, Jakeman et al. 2009, Howatson et al. 2009, Montgomery et al. 2008, Rupp et al. 2012, Yanagisawa et al. 2003, e.g.).

11.3 Criteria for the statistical use of data in the case of incomplete data sets

Only data from subjects who have completed the entire protocol will be included in the study. This ensures that all data has been collected under the same conditions and thus remains homogeneous and comparable.

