11.4 Scheduled analyses

11.4.1 Datasets and Data Populations

Only complete data sets will be included in the study. Data that contains only part of the protocol is not included in the analysis. No new subject is being sought to replace the missing data.

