11.5 Drop-outs and missing data

If a test subject does not complete the experiment, any data that has already been collected is retained, but is not further incorporated into the final data analysis.

SUPSI

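### Participants who stop because of injury or intolerance drop out of the only planned analysis, no report of harms or stops by arm is planned, and their link to the allocated application is not secured

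*Combined protocol and SAP*

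**What the plan says.** **Who leaves the analysis.** Section 8.5: "Data already collected from eliminated participants will be stored, but will not be included in the further data analysis of the study". Section 11.3: "Only data from subjects who have completed the entire protocol will be included in the study". Section 11.4.1: "Data that contains only part of the protocol is not included in the analysis". Section 11.5, on a participant who does not finish: "any data that has already been collected is retained, but is not further incorporated into the final data analysis". Section 7.4 has the same rule.

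**Which stops are foreseen.** Section 3.7 says that "there is a minimal risk of overload during the maximum jumping exercise for 1 min", names the 60% MVIC load as well, and provides for circulatory problems. Section 8.1.1 says that "the test subjects can stop the cold treatment at any time if they feel unwell", and allows the loads to be stopped too. Section 5.3 lets the examiner or the participant discontinue.

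**What is recorded.** Section 9.2.5: "if the study participation was discontinued due to an injury occurred during the study participation, this will be recorded and reported". Its list, repeated in 10.3.1, has five items: date and time, course of the incident, persons involved and witnesses, the ID assigned by the ethics committee, and personal details.

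**Where the allocation is kept.** Under 7.3 the lot shows the subject number and the application. One examiner sets the condition, tells colleagues only the number, and groups the data by application at the end. On withdrawal, 7.4 says that "the lot of the allocation is returned to the pot in a new envelope and a new participant is sought".

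**What is analysed.** Section 11.4.2 plans one repeated-measures analysis per subproject. Sections 5.3 and 9.2.4 collect nothing for safety, and 11.4.5 is a heading without text.

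**The concern.** The people who could show that an application is poorly tolerated are the people whom the exclusion rules remove. Leaving non-completers out of a repeated-measures efficacy analysis is one decision. Leaving them out of everything that is reported is another, and the plan makes both with the same sentences.

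The study aims to make recommendations for cooling applications to those who work with athletes. Readers of its results would see only participants who tolerated the whole protocol, with no count of those who did not and no split by arm. Section 2.9 also allows the study to be stopped if harm of the experimental intervention is proven, but no planned tabulation by arm would supply that evidence.

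**Working it through.** The plan gives no harm rate, expected dropout or arm split, so there is no figure of its own to reproduce. The check is mainly a comparison of sections.

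**1. Is the exclusion limited to efficacy?** No. Sections 7.4, 8.5, 11.3, 11.4.1 and 11.5 exclude non-completers without qualification. No safety set or all-randomised set is defined.

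**2. Does another analysis cover them?** No. The empty 11.4.5 is consistent with 5.3 and 9.2.4.

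**3. Is every foreseen stop recorded?**
- Stop because of an injury: yes (8.5, 9.2.5).
- Circulatory problem leading to injury: yes, as a safety-relevant event (10.3.1).
- Stop of the application or load because the participant is unwell, without injury: allowed by 8.1.1, but no record is specified. Section 9.3.2 has participants asked how they feel after the session, with no instruction to write the answer down.

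**4. Can an incident be traced to an application?** Three links are needed:
- Incident to subject number: the number is not among the five items, although personal details are.
- Subject number to application: both are on the lot (7.3), but the lot is reused (7.4). The text does not say whether the number passes to the next person who draws it.
- A lasting record of the pair: no separate allocation log is described, and 6.3 gives no procedure for keeping or breaking the code. The examiner of 7.3 must know the pairs in order to group the data, but nothing says that withdrawn participants are kept.

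**5. Scale, under assumptions.** Section 11.2 gives 20 per subproject. A 1:1 split, which is an assumption, gives n = 10 per arm. Section 10.3 speaks of 20 or fewer per experimental group, so n = 20 is shown too. The true stop rate p is assumed to be 5% to 20%.

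P(at least one stop) = 1 − (1 − p)^n

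| p | n = 10 | n = 20 |
|---|---|---|
| 5% | 1 − 0.95^10 = 40% | 1 − 0.95^20 = 64% |
| 10% | 1 − 0.90^10 = 65% | 1 − 0.90^20 = 88% |
| 20% | 1 − 0.80^10 = 89% | 1 − 0.80^20 = 99% |

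Exact (Clopper-Pearson) 95% intervals for two stops are 2.5% to 55.6% for 2/10 = 20%, and 1.2% to 31.7% for 2/20 = 10%. Under the present rules those two people would be in no planned table.

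**The case against.** The strongest reply is that harm is not lost. Injuries that end participation go to the sponsor-investigator, study leader, supervisor and insurer (8.5, 9.2.5). A safety-related event also goes to the ethics committee (10.3.2) and must be investigated before the study continues (10.3.1). All of this stands, but it is reporting of single events, and it does not put counts by arm into the results.

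A reader might go further in three ways that the documents do not support:

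- *Harm could not be reported by arm at all.* This is too strong. One examiner knows the application, withdrawn participants' data are stored, and the incident record holds personal details. The arm is recoverable in principle. What is missing is a rule that secures it.
- *The missing application on the incident form is itself a fault.* It is not. Keeping it off a form that blinded staff may see protects the blinding in 6.2.2. The link belongs in an allocation record.
- *The trial would report a harm rate of zero in the cooling arm.* It would report no harm rate. Silence is not a reported zero, though a reader may take it for one.

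Two further points stand. The population is healthy, aged 18 to 30 and screened for circulatory problems, Raynaud's syndrome and fear of cooling, so events may be rare. And the overload risk in 3.7 belongs to loads that both arms perform. In subproject A the one-minute load comes before the application (9.1), so an injury during it cannot be an effect of cooling. A table must therefore separate the stages.

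**Conclusion.** The point holds in this form: participants who stop because of injury or intolerance are outside the only planned analysis, no report of harms or stops by arm is planned, stops without injury have no specified record, and the link to the allocated application is not secured. The results would be silent on tolerability by arm.

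This should be corrected. It does not depend on any event rate. The 40% to 89% chance of at least one stop in a cooling arm is illustrative and rests on an assumed 10 per arm and an assumed true rate of 5% to 20%. Small arms limit what the correction can show: 2/10 against 0/10 gives a Fisher p of 0.474, so the purpose is a complete description and not a test.

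Two limits apply. The data collection forms listed in section 17 are not reproduced in the text available. If they already hold a field for stops or an allocation list, that part falls away, but the exclusion and the empty 11.4.5 remain. Also, 7.4 seeks a new participant after a withdrawal while 11.4.1 says none is sought. The exclusion applies under either rule, but the reuse of the lot follows from 7.4 alone.

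**What to change.** 1. In 7.4, 8.5, 11.3, 11.4.1 and 11.5, limit the exclusion of non-completers to the efficacy analysis.
2. Have the examiner who already operates the device keep a permanent list of subject number and application for everyone who draws a lot. It is made before any lot is reused, gives each person a unique entry, and is linked to the incident and stop records only after data collection ends, so that blinding is kept.
3. Add the subject number and the stage (application, load or follow-up visit) to the incident record in 9.2.5 and 10.3.1. Record every stop of the application, the load or the study, with its reason, whether or not there was an injury.
4. In 11.4.5, plan one descriptive table per subproject: injuries and stops by allocated application and stage, for everyone who drew a lot, with exact 95% intervals. Events before the application in subproject A can then be told apart.
5. Reconcile 7.4 with 11.4.1 on whether a withdrawn participant is replaced.

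The cost is a few form items, one list, one table and some wording, with no new visits, staff or measurements. The downside is that reported tolerability may look less favourable and the estimates will be imprecise. Nothing here changes the application, the loads or the rules for stopping.

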8.6 Preventive measurements

(I/IT 6.6.2; AGEK 9; SPIRIT #11d)

ICH: Medication(s)/treatment(s) permitted (including rescue medication) and not permitted before and/or during the trial.

The questionnaire asks about the intake of medication and excludes pregnancy. If static deviations are visible but not medically diagnosed, the study leader reserves the right to measure them (leg length difference, scoliosis angle) and thus exclude a test subject from participation.

8.7 Accompaniments

(I/IT 6.6.2; AGEK 9; SPIRIT #11d)

ICH: Medication(s)/treatment(s) permitted (including rescue medication) and not permitted before and/or during the trial.

No further side effects are expected from study participation.

8.8 Liability

(I/IT 6.4.7; AGEK Checklist 2, item 1; SPIRIT 11c)

ICH: Accountability procedures for the investigational product(s), including the placebo(s) and comparator(s), if any.

The experiments take place exclusively in the research laboratory of the Thim van der Laan University College Physiotherapy in Landquart. This means that there is no transport of the products and measuring instruments used. There is therefore no liability for the transport of the product .

8.9 Return of the medical device

(AGEK Checklist 2, item 1; SPIRIT 11c)

The Zamar Therapy is returned to the manufacturer after the end of the measurement period.

SUPSI

9 STUDIES STRUCTURE &

EVALUATION (ICH/E6 6.7, 6.8; AGEK 6,

7; SPIRIT #18a)

9.1 Schedules of the various protocols

1. *Subject Information & Informed Consent*

10 Min

2. *Preparation of the subject*

15 min

3. *Running the Test Log (Sublogs)*

Partial Protocol A: first measurement + intervention - approx. 60 min	
Cooling vs. Thermoneutral application on recovery	
Cooling panel	Thermoneutral Application Group
1. 3 x Vertical Leaps VAS & BARROW (max 5 min)	1. 3 x Vertical Jumps, VAS & BARROW (max 5 min)
Max 1 min break	Max 1 min break
2. 1 minute max vertical Leaps, VAS & BARROW (1 min)	2. 1 minute max vertical jumps, VAS & BARROW (1 min)
Max 5 min break	Max 5 min break
3. Cooling (20 min)	3. Thermoneutral application (20 min)
Max 1 min break	Max 1 min break
4. 3 x Vertical Leaps, VAS & BARROW (max 5 min)	4. 3 x Vertical Jumps VAS & BARROW (max 5 min)
Directly after the Intervention	immediately after the intervention
5. 3 x Vertical Leaps, VAS & BARROW (max 5 min)	5. 3 x Vertical Jumps, VAS & BARROW (max 5 min)
24 hours after the intervention	24 hours after the intervention
6. 3 x Vertical Jumps, VAS & BARROW (max 5 min)	6. 3 x Vertical Jumps, VAS & BARROW (max 5 min)
48 hours after the intervention	48 hours after the intervention
7. 3 x Vertical Leaps, VAS & BARROW (max 5 min)	7. 3 x Vertical jumps, VAS & BARROW (max 5 min)
72 hours after the intervention	72 hours after the intervention

SUPSI

Partial Protocol B: first measurement + intervention - approx. 60 min	
Cooling vs. Thermoneutral application on performance	
Cooling panel	Thermoneutral Application Group
1. 1 x MVIC, VAS & BORG (max 3 min) Max 1 min break	1. 1 x MVIC, VAS & BORG (max 3 min) Max 1 min break
2. Cooling (20 min) Max 1 min break	2. Thermoneutral application (20 min) Max 1 min break
3. 60 % MVIC for 1 min (2 min) Max 5 min break	3. 60 % MVIC for 1 min (2 min) Max 5 min break
4. 1 x MVIC, VAS & BORG (max 5 min) immediately after the intervention	4. 1 x MVIC, VAS & BORG (max 5 min) immediately after the intervention
5. 1 x MVIC, VAS & BORG (max 5 min) 24 hours after the intervention	5. 1 x MVIC, VAS & BORG (max 5 min) 24 hours after the intervention
6. 1 x MVIC, VAS & BORG (max 5 min) 48 hours after the intervention	6. 1 x MVIC, VAS & BORG (max 5 min) 48 hours after the intervention
7. 1 x MVIC, VAS & BORG (max 5 min) 72 hours after the intervention	7. 1 x MVIC, VAS & BORG (max 5 min) 72 hours after the intervention

Sub-protocol	Total time commitment	Visits
A	Approx. 80 min	Once 60 min and 3 times for max 5 min
B	Approx. 80 min	Once 60 min and 3 times for max 5 min

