Post-activity cooling (subproject A) - In this subproject, the influence of post-activity cooling compared to thermoneutral application on recovery is determined. It is investigated whether the maximum jump height changes between these interventions after maximum performance in the form of vertical jumps (1 min) and 20 min of sustained cooling or thermoneutral application (direct, 24 hours, 48 hours, 72 hours after the interventions). To investigate this, the test subjects are tested before the maximum performance (1 min vertical jumps) and again directly, 24 hours, 48 hours and 72 hours after cooling/thermoneutral application. In order to be able to determine the baseline and measure the effect of cooling compared to the thermoneutral application, the test subjects must each perform 3 vertical, maximum jumps. The maximum vertical jump height is used as an objective recovery factor in this subproject. Weilert, this subproject investigates the extent to which the subjective muscle soreness and general exhaustion data of the test subjects differ within the cooling group and thermoneutral group. To this end, before and inach the maximum performance (1 min vertical jumps) measured the subjective information of the test subjects (direct, 24 hours, 48 hours, 72 hours after cooling/thermoneutral application). A 0 - 10 VAS and 0 - 10 BORG scale is used. The VAS and BORG data are used as a subjective recovery factor in this subproject.

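### Subproject A schedules no jump test between the 1-minute load and the application, so the loss in jump height and the share of it regained cannot be estimated or checked for balance

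*Combined protocol and SAP*

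**What the plan says.** Section 3.1 gives jump height its role in subproject A: "The maximum vertical jump height is used as an objective recovery factor in this subproject". Section 4.2 lists it as the only objective recovery parameter, beside two subjective ones, muscle soreness (VAS) and general exhaustion (BORG, which the translated schedule prints as BARROW).

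The schedule for Partial Protocol A in section 9.1 runs as follows:

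- Step 1, before the load: "1. 3 x Vertical Leaps VAS & BARROW (max 5 min)".
- Step 2, the load: "2. 1 minute max vertical Leaps, VAS & BARROW (1 min)", followed by "Max 5 min break".
- Step 3, the application: "3. Cooling (20 min)", or the thermoneutral equivalent, then a break of at most 1 minute.
- Step 4, immediately after the application: "4. 3 x Vertical Leaps, VAS & BARROW (max 5 min)".
- Steps 5 to 7: the same test at 24, 48 and 72 hours.

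The narrative in section 3.1 agrees. Subjects are "tested before the maximum performance (1 min vertical jumps) and again directly, 24 hours, 48 hours and 72 hours after cooling/thermoneutral application". The synopsis and section 5.1 list only the times after the intervention.

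Section 11.1 states the jump-height hypothesis as a comparison of cooling with the thermoneutral application over a 72-hour recovery period. In sections 11.1 and 11.4.2 the Time factor has the levels 0, 24, 48 and 72 hours. The pre-load height is not among them, and no other role in the analysis is given to it.

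**The concern.** A recovery study asks how much of a loss has been made good. For the two subjective scales the plan records the state straight after the load, before the application starts. For jump height it does not.

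Three things are then missing for the objective outcome: the size of the acute loss, the share of it regained by step 4, and an objective check that the load lowered jump height to a similar degree in both arms. The check matters because section 8.1.1 lets participants stop the load whenever they reach their personal limit, so the fatigue produced may vary between people. It matters most for a null result. If both arms are back at the step 1 level by step 4, the data cannot separate full recovery from a load that never reduced jump height.

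**Working it through.** The plan gives no figure for this point that could be reproduced. Section 11.2 justifies 20 subjects by the group sizes of comparable studies and states no effect size, SD or power.

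**Time from the load to the first jump test** (section 9.1). Break of 0 to 5 min + application of 20 min + break of 0 to 1 min.

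- Shortest: 0 + 20 + 0 = 20 min.
- Longest: 5 + 20 + 1 = 26 min.

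**What can be derived.** Let B be the pre-load height, L the loss caused by the load, and Y the height at step 4.

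- Remaining deficit = B − Y. Both terms are measured, and the same holds at 24, 48 and 72 h.
- Share regained = 1 − (B − Y)/L. L is not measured.

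Take illustrative (assumed) heights B = 40 cm and Y = 38 cm, a deficit of 2 cm:

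| Loss L (cm) | Share regained |
|---|---|
| 2 | 1 − 2/2 = 0% |
| 4 | 1 − 2/4 = 50% |
| 6 | 1 − 2/6 = 67% |
| 10 | 1 − 2/10 = 80% |

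The same two measured heights fit anything from no recovery to 80% recovery.

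**Chance imbalance in the unmeasured loss.** For n per arm, SE = SD × √(2/n), where SD is the between-person SD of the loss. The documents do not give it. They also leave n open: 20 subjects in subproject A over two arms is about 10 per arm (section 11.2; allocation ratio not stated), while section 10.3 speaks of 20 or fewer in each experimental group.

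| n per arm | SE | 95% range (±1.96 SE) | SE if SD is 2 to 4 cm (assumed) |
|---|---|---|---|
| 10 | √(2/10) = 0.45 SD | ±0.88 SD | 0.9 to 1.8 cm |
| 20 | √(2/20) = 0.32 SD | ±0.62 SD | 0.6 to 1.3 cm |

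**What adjustment could gain.** An illustrative simulation (8,000 repetitions per setting) used only assumed values: pre-load height 40 cm with between-person SD 6 cm; mean loss 6 cm with SD 1.5 or 3 cm; test error SD 1.5 cm; shares regained of 0.7 and 0.5. The true group difference is then 6 × (0.7 − 0.5) = 1.2 cm. All three analyses returned about 1.2 cm on average, so none was biased. The SE of the estimated group difference was:

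| n per arm | No covariate | Pre-load height | Pre-load and post-load height |
|---|---|---|---|
| 10 | about 2.8 cm | 1.00 to 1.12 cm | 0.88 cm |
| 20 | about 2.0 cm | 0.70 to 0.79 cm | 0.61 cm |

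Most of the gain comes from the pre-load height, which is already collected. The post-load test adds a smaller one. At 10 per arm it is worth (1.00/0.88)² = 1.29 to (1.12/0.88)² = 1.62 times the sample size, under these assumptions only.

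**The case against.** The strongest reply is that the stated hypothesis does not need the missing value. It compares two arms over 72 hours. Allocation is by lot, participants and examiners are to be blinded, and the load comes before the application, so the loss is a pre-treatment variable. Chance imbalance in it causes no bias and is already part of the between-person error. This stands.

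A reader might infer from the gap that recovery of jump height cannot be derived at all. The documents do not support that. Step 1 supplies a pre-load height, which section 3.1 names as the baseline, so return towards it can be calculated for each person at every later time.

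A reader might also infer that nothing shows how fatigued the arms were before the application, or that the load had any effect. That too goes too far. VAS and BORG are taken at step 2 in both arms, which gives a subjective check. Comparing step 1 with steps 4 to 7 in the thermoneutral arm would reveal a deficit that lasts. Only a drop that disappears within about 20 to 26 minutes goes unseen.

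Finally, section 9.2.1 says in general terms that the listed data, jump height among them, are collected during all tests in section 9.1, and the measurement form is an appendix that is not reproduced. The supportable statement is therefore that no jump test is scheduled at this point, not that no height could be recorded there. The reply does not remove the gap: section 9.1, section 3.1, the synopsis and section 5.1 give no time for a jump height between load and application.

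**Conclusion.** The point holds as a limited design gap. For subproject A's only objective outcome, the acute loss, the share regained and an objective check of the load in each arm are unavailable. The remaining deficit from the pre-load height is available, and the between-arm comparison remains valid.

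The cost is unobserved chance imbalance in the loss, with SE 0.45 SD at 10 per arm or 0.32 SD at 20 per arm. The translation to 0.9 to 1.8 cm, or 0.6 to 1.3 cm, rests on an assumed SD of 2 to 4 cm. It describes imbalance just after the load, and how much of that carries through to 24 to 72 hours is unknown. The documents state no expected cooling effect to set it against. The simulated precision gains likewise rest wholly on assumed values.

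This is a cheap improvement to make before data collection, since the post-load height cannot be obtained afterwards. It does not invalidate the primary comparison.

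**What to change.** In section 9.1, Partial Protocol A, add the same test of three vertical jumps at the start of the existing break after step 2, before the application and identically in both arms. Carry the added time point into the synopsis and sections 3.1 and 5.1. Use the three separate jumps rather than the last jumps of the 1-minute bout, because continuous jumping is a different task and its difference from step 1 would not be a clean loss.

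In section 11.4.2, state two uses: a description by arm of the drop from step 1, as a check that the load lowered jump height; and the step 1 and post-load heights as covariates in the jump-height analysis. The step 1 covariate should be added even if the extra test is not, since it costs nothing to collect.

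Cost: three more jumps per person, a small added load that is equal in both arms, and one more field on the measurement form.
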